## 4. General Principles of Statistical Analysis

- Statistical tests will be performed using a two-sided significance level of 5%.
- Summary statistics will include the number of subjects, mean, standard deviation, minimum, median, maximum, and quartiles.
- Unless otherwise specified, data will be summarized for each analysis group, each period, and each analysis visit.
- For confidence intervals (CIs) of proportions, Clopper-Pearson exact two-sided 95% CIs will be presented for each group, and Chan-Zhang exact two-sided 95% CIs will be presented for between-group differences.

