## 6.3 Interim Analyses and Data Monitoring

### 6.3.1 Timing of analysis

#### 1) First data cutoff

After all subjects have completed Period I, the following data collected by the first data cut-off date will be analyzed for Period I, long-term treatment of R788, R788 treatment period, and the

- Period I data of all subjects
- Period II data of subjects who completed Period II
- Follow-up data of subjects who completed the follow-up period

2) Second data cutoff

After all subjects have completed the non-dosing period, all data collected by the second data cut-off date will be analyzed for Period I, long-term treatment of R788, Period II, non-dosing period, Period III, R788 treatment period, and the entire study period.

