- Elapsed time after administration = Time of blood sampling – Time of study drug administration
- Treatment compliance = Total number of administered tablets / Number of prescribed tablets × 100

- Number of prescribed tablets

Defined as the sum of the products of the number of tablets prescribed per day and the duration of treatment. However, if dose interruption due to an AE or any other reasons occurs during a period other than the non-dosing period, the dose prescribed immediately before the dose interruption will be applied.

- Treatment dose at each analysis visit

Defined as the dose at the time of measurement of platelet count. For Day 1 of Period I, Week 24 of Period II, and Day 1 of Period III, the initial doses for each period will be used. If the study drug is interrupted on the relevant day, the dose will be categorized as interruption. Analysis visits after treatment discontinuation will be excluded from the analysis.

- Average daily dose

Defined as the weighted average of treatment dose, with the duration of exposure at each dose as the weighting factor. Dose interruption will be handled as 0 mg dose.

- Duration of platelet response = End day of response – Start day of response + 1

The start day of response is defined as the first day after the start of study treatment in each period on which a platelet count of  $\geq 50000/\mu\text{L}$  for at least 28 consecutive days without the use of rescue medications was achieved. The end day of response is defined as the day of use of a rescue medication or the first day of the period in which the platelet count fell below  $50000/\mu\text{L}$  for at least 28 consecutive days, whichever is earlier. For subjects who discontinue or complete each period with the platelet count maintained at  $\geq 50000/\mu\text{L}$ , the last measurement day in each period is defined as the end day of response. The calculation of the duration of platelet response includes analysis visits outside the acceptable time window and unscheduled visits.

- Sustained stable platelet response

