#### **11.2.1.3 Duration of platelet response**

Summary statistics will be presented.

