### **11.2.6.2 Duration of platelet response**

Summary statistics will be presented. The non-dosing period will be included in the evaluation of the duration of platelet response. This assessment will be performed for the R788 group, R788-R788 group, and P-R788 group.

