## 11.3 Subgroup Analysis of Efficacy

- 1) The analyses described in “[11.2.6.1 Platelet response rate](#)” will be performed for each line of therapy (2nd line, 3rd line or later).
- 2) At the first data cut-off, the analyses described in “[11.2.2.1 Achievement rates for platelet count-related endpoints](#)” will be performed, excluding subjects who are still in Period II.
- 3) Summary statistic of platelet count in “[11.2.1.4 Summary statistics of platelet count](#)” will be presented for responders and non-responders in stable platelet response. Additionally, medians and quartiles will be presented graphically for responders and non-responders in the R788 group, and for the placebo group.
- 4) For the data in Period I, the median platelet count after the administration of the investigational product will be calculated for each subject, and the summary statistics will be presented for the R788 group, for responders and non-responders in stable platelet response in the R788 group, and for the placebo group.

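### The duration-of-response tables treat responses that were still ongoing as if they had ended, so the mean is too low and the median can be

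*SAP*

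**What the plan says.** Duration of platelet response is end day minus start day plus 1 (SAP section 7). On the start, "The start day of response is defined as the first day after the start of study treatment in each period" that opens at least 28 consecutive days at or above 50000/µL without rescue. The end is the earlier of rescue use and the first day of a run of at least 28 days below 50000/µL. A further rule covers responses with neither event. "For subjects who discontinue or complete each period with the platelet count maintained at" or above that threshold, "the last measurement day in each period is defined as the end day of response".

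The duration tables are in SAP 11.2.1.3 (Period I), 11.2.2.2 (long-term treatment), 11.2.3.3 (Period II) and 11.2.6.2 (R788 treatment period). Each asks for summary statistics only; the first reads in full "Summary statistics will be presented". SAP section 4 says what that means: "Summary statistics will include the number of subjects, mean, standard deviation, minimum, median, maximum, and quartiles". For the R788 treatment period, "The non-dosing period will be included in the evaluation of the duration of platelet response".

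At the first data cutoff (SAP 6.3.1) the later data come in only as "Period II data of subjects who completed Period II". SAP 11.3 item 2 repeats the long-term achievement-rate analysis, which "will be performed, excluding subjects who are still in Period II". It does not do so for duration.

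The swimmer plots (SAP 11.2.1.6, reused in 11.2.2.5, 11.2.3.6 and 11.2.6.3) do mark a continued response separately from the end of maintenance.

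**The concern.** A response with no end event by the last measurement is right-censored: its true length is at least the recorded value. The SAP's plots make that distinction and its tables drop it.

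Duration is secondary endpoint 6. It bears on the objective of maintaining platelet count under long-term R788, and protocol 4.1.2 says it was chosen to allow comparison with the overseas studies. Under this rule the tabulated figure depends on length of follow-up as well as on the drug, and a reader of the table alone cannot tell truncation from loss of response.

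Two cases are also left without an end day:

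- **A final dip shorter than 28 days.** In Period I, a fall first seen at Week 22 or 24 cannot reach 28 days, yet the count was not maintained either.
- **Subjects still in Period III at the second cutoff.** The rule names only discontinuation and completion, while SAP 8.2 classes such subjects separately as ongoing.

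**Working it through.** The plan gives no figure for duration to reproduce. All durations below are assumed.

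**1. Mean.** Let T be the full duration and C the time from response start to the last measurement. The SAP records X = min(T, C). X is below T for every ongoing response, so a mean of X is below the mean of T whenever at least one response is ongoing.

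**2. Median.** It falls only if ongoing values lie below it. There are three routes: late starts, because the clock starts on each subject's own response day; early discontinuation; and, at the first cutoff only, a responder still in Period II being cut at Week 24 in the long-term table.

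**3. Example on the Period I visit grid** (Week x is Day 7x + 1, SAP Table 5.9-2).

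- Three responders start at Week 2 (Day 15) and end at Weeks 12, 16 and 20 (Days 85, 113, 141): 71, 99 and 127 days.
- Two start at Weeks 16 and 18 (Days 113, 127) and are still responding at Week 24 (Day 169): 57+ and 43+ days.
- SAP table, 40% ongoing: mean (71 + 99 + 127 + 57 + 43)/5 = 397/5 = 79.4; median 71.
- Kaplan-Meier: survival is 2/3 after Day 71, 1/3 after Day 99 and 0 after Day 127. Median 99; mean 71 + 28(2/3) + 28(1/3) = 99.0.
- Without the 57+ subject (25% ongoing): SAP mean 340/4 = 85.0, median (71 + 99)/2 = 85; Kaplan-Meier unchanged.

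**4. Model with known truth** (weeks). T = 4 + exponential with mean m − 4; onset uniform Week 2 to 12; no dropout. The true median is 4 + (m − 4) ln 2. C is uniform on [a, b], which is [12, 22] for a Week 24 cut and [40, 50] for Week 52. The ongoing share is p = ((m − 4)/10)(e^(−(a−4)/(m−4)) − e^(−(b−4)/(m−4))), and the reported mean is 4 + (m − 4)(1 − p). For m = 52 in Period I: p = 4.8(0.8465 − 0.6873) = 0.764, mean 4 + 48(0.236) = 15.3. Reported medians are from 1,000,000 simulated responders per case.

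| True mean / median | Period I mean / median / ongoing | To Week 52 mean / median / ongoing |
|---|---|---|
| 20 / 15.1 | 12.8 / 13.1 / 45% | 18.7 / 15.1 / 8% |
| 26 / 19.2 | 13.7 / 14.1 / 56% | 22.6 / 19.2 / 16% |
| 52 / 37.3 | 15.3 / 15.6 / 76% | 31.5 / 37.2 / 43% |
| 104 / 73.3 | 16.2 / 16.3 / 88% | 37.6 / 42.6 / 66% |

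The Week 52 columns take the long-term evaluation as one period. With onset uniform Week 2 to 20 instead, Period I medians are 9.4, 10.1, 11.5 and 12.2 (60%, 68%, 83% and 92% ongoing). Week 52 medians are 15.1, 19.2, 33.4 and 37.4, with 47% ongoing in the third case.

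**5. Median with fewer ongoing** (days; T = 28 + exponential).

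| Setting | True median | Ongoing | SAP median |
|---|---|---|---|
| Period I, starts over Weeks 2–20 | 42 | 20% | 39.9 |
| same | 56 | 33% | 47 |
| Period I, starts Weeks 2–6, 20% assigned early discontinuation | 56 | 12% | 54 |
| same | 84 | 31% | 76.6 |
| Period II, starts at its Weeks 4–24 | 56 | 33% | 48.6 |

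Counter-case: with all starts at Week 2 and no discontinuation, the median is unbiased at 21% and 39% ongoing, while the mean is already 16% and 32% low.

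**6. Size of the final-dip gap.** In the step 4 model a fall between Weeks 20 and 24, which cannot meet the 28-day end rule within Period I, occurs in 13%, 11%, 7% and 4% of responders.

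**The case against.** - **The median effect is conditional.** In the step 4 model with onset to Week 12 the median is unbiased up to 43% ongoing, and the Week 52 median is essentially right in the first three rows. The five-subject example is constructed so that only late starters are ongoing, and its Kaplan-Meier mean is just the mean of the three completed responses. This stands as a limit: the claim is that the median can be low, and step 5 shows it with 12% to 33% ongoing. The 12% and 20% cases move it by only about 2 days.
- **The first-cutoff problem resolves.** SAP 6.3.1 re-analyses long-term treatment after all subjects have finished the non-dosing period. That is right; the Week 24 cut affects only the earlier table.
- **For a subject who discontinues, ending the response at the last count is a defensible on-treatment definition.** SAP 11.1 counts discontinuation for an adverse event or lack of efficacy as non-response. This is a fair choice of estimand, which is why the fix includes that version. It does not cover subjects who complete a period still responding.
- **Much is already visible.** The protocol prespecifies summary statistics, SAP 11.2.2.1 gives proportions at fixed weeks, the 11.2.6.2 table spans periods, and with 24 subjects planned the ongoing responses can be counted from the swimmer plots. Labels may also sit in the table shells, which SAP section 15 says are separate. All true, but none of it corrects the tabulated mean or median, or supplies the two missing end-day rules.

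**Conclusion.** The concern holds. Read as response duration, the tabulated mean is biased downwards whenever any response is ongoing; this follows from the definition and needs no model. The median is biased when enough ongoing durations fall below it, which needs late starts, early discontinuation or roughly half or more ongoing. In the assumed model with a true mean of 52 weeks, the same drug effect is reported as a mean of 15.3 weeks in Period I and 31.5 weeks to Week 52. The actual size is unknown, because the documents give no expected durations, onset times or number of 28-day responders.

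Consequences are confined to the four duration tables. SAP 6.5.1 and 6.5.2 make everything except the primary endpoint reference only, and the Fisher test on stable platelet response is untouched. This is a change worth considering, not a threat to the trial's main conclusion.

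**What to change.** In SAP section 7:

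- Flag as censored any responder with neither rescue use nor a fall of at least 28 days, including those still on treatment at a data cutoff.
- State how a final dip shorter than 28 days is handled, for example censored at the last count at or above 50000/µL, with a check that counts it as an end.

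In the four duration tables:

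- Keep the protocol's summary statistics, label them observed duration, and add a row for the number ongoing.
- Add Kaplan-Meier estimates: the proportion still responding at fixed weeks, and the median where estimable.
- Add a sensitivity analysis counting discontinuation for an adverse event or lack of efficacy as the end of response, in line with SAP 11.1.

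The cost is some wording, two table rows and one survival procedure on data already derived for the swimmer plots. The drawback is that the Kaplan-Meier median may not be reached. For an assumed 3 to 8 responders under the step 4 model, it is estimable in 94–100%, 63–79% and 24–30% of trials by Week 52, for true means of 26, 52 and 104 weeks. In Period I the figures are 47–57%, 17–22% and 5–10%. The label and the number ongoing are useful in every case.

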## 8. Disposition of Subjects

### 8.1 Analysis Sets

Applicable period: Period I

For all randomized subjects, the number and percentage of subjects included in or excluded from the analysis sets listed in [Table 8.1-1](#) will be presented. Differences between groups will be analyzed using Fisher's exact test.

Table 8.1-1

Category

Analysis set	Category
FAS	Included, Excluded
SS	Included, Excluded
PKS	Included, Excluded

## 8.2 Discontinuation and Reasons for Discontinuation

Applicable period: Period I, long-term treatment of R788, Period II, Period III, and R788 treatment period

The number and percentage of subjects who discontinued the study will be presented. In Period I, differences between groups will be analyzed using Fisher's exact test. Subjects who are ongoing in the applicable period at the time of data cut-off will be categorized as "Ongoing."

Reasons for discontinuation will be classified into the following categories, and the number and percentage of subjects will be presented.

Evaluation during long-term treatment of R788 includes whether there were discontinuations after transition to Period II and their reasons. For evaluation in Period II, the number of subjects who completed Period I or early transitioned to Period II will also be presented.

- Adverse events: Withdrawal due to Withdrawal Criteria (withdrawal in individual subjects)  
1) "Adverse Events"
- Lack of efficacy: Withdrawal due to Withdrawal Criteria (withdrawal in individual subjects)  
2) "Lack of Efficacy (inadequate response)"
- Withdrawal by subject: Withdrawal due to Withdrawal Criteria (withdrawal in individual subjects)  
3) "Subject's voluntary request for withdrawal from the study"
- Significant deviation: Withdrawal due to Withdrawal Criteria (withdrawal in individual subjects)  
4) "Significant deviation from the protocol during the study period"
- Other: When the reason for discontinuation does not correspond to "adverse event," "lack of efficacy," "withdrawal by subject" or "significant deviation" in this category.

## 9. Demographics and Other Baseline Characteristics

### 9.1 Subject Demographics

Applicable period: Period I, R788 treatment period

The variables to be analyzed are listed below. The pooled analysis of R788 and placebo groups will be performed only for Period I. For both Period I and the R788 treatment period, data from Day 1 of Period I will be used for analysis.

- Nominal scale variables
  - Sex: Male, female
  - Splenectomy: Yes, no
  - Prior ITP medications: Corticosteroids, rituximab, thrombopoietin receptor agonists, intravenous immunoglobulins, immunosuppressants, other
- Ordinal scale variables
  - Age: < 65 years, ≥ 65 years
  - Time since ITP diagnosis: < 3 years, ≥ 3 years
  - Time since splenectomy: < 6 months, ≥ 6 months

- Number of unique prior ITP medications (categories): 1, 2, 3,  $\geq 4$
- Number of unique prior ITP medications (drugs): 1, 2, 3, 4, 5,  $\geq 6$
- Line of therapy: 2,  $\geq 3$
- Platelet count:  $< 15000$ ,  $15000 \leq < 30000$ ,  $30000 \leq < 35000$ ,  $\geq 35000/\mu\text{L}$
- Continuous variables: Age, height, weight, body mass index (BMI), time since ITP diagnosis (years), time since splenectomy (months), number of unique prior ITP medications (categories), number of unique prior ITP medications (drugs), line of therapy, platelet count

The numbers and percentages of subjects will be presented for nominal and ordinal scale variables, and summary statistics for continuous variables.

Subjects who have not undergone splenectomy will be excluded from the evaluation of time since splenectomy.

## **9.2 Complications and Medical History**

Applicable period: Period I

The numbers and percentages of subjects will be presented for the entire population and by primary SOC and PT.

## **9.3 Prior ITP medications**

Applicable period: Period I

For medications used for the treatment of ITP before study drug administration, the numbers and percentages of subjects who used such drugs will be presented.

## **9.4 Concomitant Medications Used for Complications**

Applicable period: Period I, long-term treatment of R788, Period II, and non-dosing period  
For medications used to treat complications after study drug administration, the numbers and percentages of subjects who used such drugs will be presented.

# **10. Treatment compliance**

## **10.1 Duration of Exposure**

Applicable period: Period I, long-term treatment of R788, Period II, non-dosing period, Period III, and R788 treatment period

Summary statistics will be presented. For the non-dosing period, the duration of dose interruption will be presented.

## **10.2 Distribution of Duration of Exposure**

Applicable period: Period I, long-term treatment of R788, Period II, non-dosing period, Period III, and R788 treatment period

The variables to be analyzed are as follows:

- Duration of treatment (Period I):  $<4$ ,  $4 \leq <8$ ,  $8 \leq <12$ ,  $\geq 12$  weeks
- Duration of treatment (long-term treatment of R788):  $<4$ ,  $4 \leq <8$ ,  $8 \leq <12$ ,  $12 \leq <24$ ,  $\geq 24$  weeks

- Duration of treatment (Period II):  $<4$ ,  $4 \leq <8$ ,  $8 \leq <12$ ,  $12 \leq <24$ ,  $\geq 24$  weeks
- Duration of dose interruption (non-dosing period):  $<4$ ,  $\geq 4$  weeks
- Duration of treatment (Period III):  $<24$ ,  $24 \leq <48$ ,  $48 \leq <72$ ,  $\geq 72$  weeks
- Duration of treatment (R788 treatment period):  $<4$ ,  $4 \leq <8$ ,  $8 \leq <12$ ,  $12 \leq <24$ ,  $24 \leq <52$ ,  $\geq 52$  weeks

The numbers and percentages of subjects will be presented. The duration of dose interruption will be presented for the non-dosing period.

## **10.3 Treatment Compliance**

Applicable period: Period I, long-term treatment of R788, Period II, Period III

Summary statistics will be presented. The evaluation in Period III will be conducted at study completion only.

## **10.4 Daily Dose**

Applicable period: Period I, long-term treatment of R788, Period II, Period III

- Dose: 100, 150, 200, and 300 mg/day, withdrawal

The numbers and percentages of subjects treated with each dose level will be presented.

## **10.5 Average Daily Dose**

Applicable period: Period I, long-term treatment of R788, Period II, Period III, and R788 treatment period

Summary statistics will be presented.

## **10.6 ITP Concomitant Medications**

Applicable period: Period I, long-term treatment of R788, Period II, non-dosing period, Period III, and R788 treatment period

For medications used to treat ITP after study drug administration (excluding rescue medications), the numbers and percentages of subjects who used such drugs will be presented.

## **10.7 Rescue Medications**

Evaluation will be made for all rescue medications and for each indication (increased platelet, other).

### **10.7.1 Use of rescue medications**

Applicable period: Period I, long-term treatment of R788, Period II, non-dosing period, Period III, and R788 treatment period

For rescue medications used after study drug administration, the numbers and percentages of subjects who used such medications will be presented.

### **10.7.2 Frequency of rescue medication use**

Applicable period: Period I, long-term treatment of R788, Period II

The number and percentage of subjects by the frequency of rescue medication use will be presented. The type of rescue medications will not be considered.

### **10.7.3 Use of rescue medications (in each period)**

Applicable period: Period I, long-term treatment of R788, Period II

The numbers and percentages of subjects who used rescue medications after study drug administration will be presented every 2 weeks for Period I and every 4 weeks for Period II. Subjects who used rescue medications across two or more periods will be considered to have used those medications throughout all applicable periods.

## **11. Efficacy**

### **11.1 Primary Endpoint**

Applicable period: Period I

The primary efficacy endpoint in this study is the achievement rate of stable platelet response. The analysis of the primary endpoint will be based on data from Period I.

Stable platelet response: Subjects who achieve a platelet count of  $\geq 50000/\mu\text{L}$  at 4 or more of the 6 visits from Weeks 14 to 24 will be considered as responders, and the percentage of responders will be evaluated.

Whether a subject has achieved stable platelet response will be evaluated according to the following rules:

- Subjects who discontinued due to an AE or lack of efficacy and those who used rescue medications between Week 10 and Week 24 will be considered as non-responders.
- Missing data in subjects other than those listed above will be imputed by LOCF until Week 24, and whether stable platelet response has been achieved will be determined based on the imputed data.

#### **11.1.1 Analysis methods for the primary endpoint**

The number and percentage of subjects achieving stable platelet response and their two-sided 95% CIs will be presented. The difference in the achievement rate between groups and its two-sided 95% CI will be calculated. The superiority of the R788 group to the placebo group will be evaluated using Fisher's exact test.

## **11.2 Secondary Endpoints**

### **11.2.1 Evaluation in Period I**

Applicable period: Period I

#### **11.2.1.1 Achievement rates for platelet count-related endpoints**

The variables to be analyzed are as follows:

- Achievement rate of a platelet count of  $\geq 50000/\mu\text{L}$  at Weeks 12 and 24
- Achievement rate of a platelet count of  $\geq 30000/\mu\text{L}$  and change from the baseline in platelet count of  $\geq 20000/\mu\text{L}$  at Weeks 12 and 24 (for subjects with a baseline platelet count of  $< 15000/\mu\text{L}$ )

- Achievement rate of overall response (subjects who achieve a platelet count of  $\geq 50000/\mu\text{L}$  at 1 or more of the 6 visits from Weeks 2 to 12 will be considered as responders, and the percentage of responders will be evaluated)

The number and percentage of responders and their two-sided 95% CIs will be presented. The difference in the achievement rate between groups and its two-sided 95% CI will be presented. All subjects who are not assessed as responders due to discontinuation or missing data will be considered as non-responders.

